2.3.3 Baseline pharmacodynamics parameters

Baseline values for sphingomyelin and sphingomyelin metabolites, including, but not limited to, ceramide in dried blood spots (DBS), lyso-sphingomyelin and sphingosine-1-phosphate in plasma and/or DBS will be the last available value before first infusion; typically these will be the screening values.

Baseline pharmacodynamic data will be presented along with subsequent pharmacodynamics values assessed during or after olipudase alfa dosing using pharmacodynamic population.

2.4 EXTENT OF STUDY TREATMENT EXPOSURE AND COMPLIANCE

The extent of study treatment exposure will be assessed and will be summarized using safety population. The duration of exposure is defined as the number of weeks between first infusion and disposition date (ie, the end of study date) in the study: (disposition date of the study – first infusion date + 1)/7. The number of infusions received and the duration of exposure will be summarized by age cohorts and overall.

The distribution of weeks on study treatment (<12 weeks, >=12 weeks to <26 weeks, >=26 weeks to <38 weeks, >=38 weeks to <52 weeks, >=52 weeks to <64 weeks, and >=64 weeks) will be provided using number and percentage of patients by age group cohorts and overall.

Compliance to the treatment regimen will be monitored in terms of the percentage of scheduled infusions the patient receives during the treatment period. A patient is considered noncompliant if the patient missed 2 or more consecutive infusions (not-for-cause, such as when the missed infusions are required by the protocol due to a dose limiting toxicity) or a total of 4 or more infusions for the 64-week treatment period. Whether a missed infusion is for-cause or not will be reviewed and determined by the clinical team; the decision will be used in the analysis of compliance.

Overall Compliance = $100\% \times \text{Total number of infusions received} / \text{Total number of expected infusions}$

where total number of expected infusions refers to the number of infusions expected between the first infusion and the date of withdrawal or date of completion. It is calculated as the integer part of (Date of withdrawal – Date of the first infusion)/14. For a patient who completes the 64-week treatment period, the total number of expected infusions is 33.

Compliance excluding for-cause = $100\% \times \text{Total number of infusions received} / \text{Total number of expected infusions (excluding for-cause missing infusions)}$

where total number of not-for-cause expected infusions refers to the number of infusions expected between the first infusion and the date of withdrawal or date of completion, excluding the

for-cause missed dose. It is calculated as the integer part of [(Date of withdrawal – Date of the first infusion)/14] – number of for-cause missed infusions.

Overall compliance and compliance excluding for-cause will be summarized descriptively as quantitative variable by age group cohorts and overall using safety population. The numbers and percentages of patients whose compliance are <80%, >=80% to <90%, >=90% to <100% and >=100% will be provided. Number and percentage of patients in the following two categories will be presented:

- Missed 2 or more not-for-cause consecutive infusions.
- Missed 4 or more scheduled infusions.

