### **8.3.2 Investigational medicinal product administration**

For all dose levels, dosing with olipudase alfa is by intravenous infusion every 2 weeks ( $\pm 3$  days). The dose escalation phase and the 64-week treatment period begin with the first intravenous infusion of 0.03 mg/kg olipudase alfa on Day 1/Week 0 ([Section 1.1](#)). All subsequent olipudase alfa administrations are to be scheduled relative to the Day 1/Week 0 visit. The dose escalation phase ends with the first infusion at 3.0 mg/kg or with the identification of a patient-specific highest tolerated dose.

Patients who tolerate the 0.03 mg/kg dose at Day 1/Week 0 (one re-challenge of the 0.03 mg/kg dose is allowed) will receive a dose of 0.1 mg/kg 2 weeks later. Patients who tolerate the 0.1 mg/kg dose (one re-challenge of the first 0.1 mg/kg dose is allowed) will receive a dose of 0.3 mg/kg dose 2 weeks later. Patients tolerating 2 consecutive doses of 0.3 mg/kg will be dose escalated step-wise to receive 2 consecutive doses at 0.6 mg/kg, followed by infusions at 1.0 mg/kg and 2.0 mg/kg, and to the final target dose of 3.0 mg/kg, which is maintained for the remaining duration of the treatment period. Patients unable to tolerate 3.0 mg/kg olipudase alfa will receive the highest tolerable dose every 2 weeks until the end of the treatment period. (Refer to [Section 8.3.4.2.1](#) for patient stopping criteria.)

Decisions regarding dose escalations may be made by discussion between the investigator and the sponsor upon review on an individual patient basis. See [Section 8.3.4](#) for dose escalation criteria.

All infusions will take place in a monitored setting with ready access to emergency resuscitation equipment and medications.

Patients will receive intravenous olipudase alfa over a period of approximately 20 minutes to 4.5 hours, depending on the dose. The length of the infusion time may be adjusted based on the patient's tolerance of the infusion.

Infusions should be administered at approximately the same time of the day. There are no restrictions on the infusion timing with respect to meals.

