### **8.3.3 Infusion delays or missed infusions**

During the treatment period, patients are infused with olipudase alfa every 2 weeks ( $\pm 3$  days) with all olipudase alfa infusions scheduled relative to the first study infusion on Day 1/Week 0. If any olipudase alfa infusion is delayed by more than 3 days, the infusion is considered a missed infusion. Missed infusions should not be administered. The patient should return to the clinic for their next scheduled visit and receive their last previously tolerated dose level of olipudase alfa. If more than 1 infusion is missed during dose escalation, the next dose will be decreased by 1 level. If more than 1 infusion is missed after the patient has completed dose escalation, the last previously tolerated dose level of olipudase alfa may be administered or the dose may be decreased by 1 level at the investigator's discretion.

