### **8.3.4 Escalation schema including dose-limiting toxicity criteria and maximally tolerated dose determination**

#### **8.3.4.1 Dose escalation schema**

During dose escalation, patients will undergo in-patient hospitalization as indicated in [Section 10.3.1](#). The following criteria will determine the next dose of olipudase alfa to be administered, provided the patient does not experience an AE that meets the patient stopping criteria (see [Section 8.3.4.2.1](#)). Only AEs not related to the patient's underlying condition will affect dose escalation. These criteria apply to AEs considered related to study treatment.

1. If the patient experiences no AE or a mild AE, escalate to the next dose.
2. If the patient experiences a moderate AE, repeat the same dose. Note: Re-challenge for patients with a moderate AE at a dose of 0.03 or 0.1 mg/kg olipudase alfa is permitted only once before the patient is discontinued from the study and replaced.
3. If the patient experiences a severe AE, decrease to the prior dose. Note: Patients with a severe AE at a dose of 0.03 mg/kg or 0.1 mg/kg olipudase alfa will be discontinued from the study and replaced. Re- challenge for patients with a severe AE at a dose of 0.3 mg/kg olipudase alfa is permitted only once (at the lower dose of 0.1 mg/kg) before the patient is discontinued and replaced.

If a patient presents on the day of infusion either with an unresolved AE or an acute illness, neither of which meets the patient stopping criteria ([Section 8.3.4.2.1](#)), the olipudase alfa infusion may be withheld or administered at the discretion of the investigator. If it is not possible to administer a regularly scheduled infusion within the 3-day window allowed per protocol, see [Section 8.3.3](#).

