#### **8.3.4.2 Dose-limiting toxicity criteria**

For the purpose of this study, the events listed under patient stopping criteria (see [Section 8.3.4.2.1](#)) are considered indicative of a potential DLT for olipudase alfa at a given dose. If a potential DLT is observed, dosing will be temporarily stopped in an individual patient or in the entire study, and the DMC will review the safety data. The DMC will then provide recommendation(s) to the sponsor regarding further patient treatment ([Section 6.3](#)). Screening for eligible patients may continue during DMC review of patient or study stopping events.

When olipudase alfa dosing is temporarily halted for a particular patient, safety monitoring of the patient will continue. If the AE(s) is/are reversible and the clinical laboratory tests (including liver function tests) have reached pre-event levels, the patient will resume dosing and receive the previously-tolerated lower dose. Depending on the patient's response, dose escalation will either continue (as described in [Section 8.3.4.1](#)) or the patient will remain at the previously tolerated dose (ie, the patient's highest tolerated dose [HTD]).

The investigator is responsible for notifying his/her Institutional Review Board/Independent Ethics Committee (IRB/IEC) in writing when a potential DLT is being evaluated at his/her investigative site.

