2.6.1.6 Adverse events leading to permanent treatment discontinuation

In this study, if the treatment is discontinued permanently, the patient is withdrawn from the study. A temporary dose interruption is not considered permanent discontinuation of study treatment. AEs leading to permanent treatment discontinuation will be provided as part of the patient narrative.

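### The SAP's expected-infusion formula for withdrawn patients leaves out the Day 1 infusion, so their compliance can exceed 100% and is on a different basis from the 33 used for completers

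*SAP*

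**What the plan says.** SAP 2.4 defines overall compliance as 100% times infusions received over infusions expected between the first infusion and withdrawal or completion. For the denominator it says: "It is calculated as the integer part of (Date of withdrawal – Date of the first infusion)/14". It then says: "For a patient who completes the 64-week treatment period, the total number of expected infusions is 33".

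A second measure excludes infusions missed for cause. Its denominator reuses the same term: "It is calculated as the integer part of [(Date of withdrawal – Date of the first infusion)/14] – number of for-cause missed infusions". No separate completer value is given there.

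Protocol 8.3.2 starts dosing on Day 1/Week 0 at two-week intervals with a ±3-day window, and adds: "All subsequent olipudase alfa administrations are to be scheduled relative to the Day 1/Week 0 visit". On lateness, Protocol 8.3.3 says: "If any olipudase alfa infusion is delayed by more than 3 days, the infusion is considered a missed infusion".

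Protocol 11.4.1.1 requires the percentage of patients below 80% compliance. SAP 2.4 reports four bands (below 80%, 80% to below 90%, 90% to below 100%, and 100% or more) by age cohort and overall in the safety population.

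**The concern.** Infusions fall at Weeks 0, 2, 4 and so on, so the number due by a given day is the number of completed 14-day intervals plus one. The withdrawal formula has no plus one, yet the numerator counts the Day 1 infusion for everyone. The SAP's own 33 for completers does include Day 1, so one summary table would mix two conventions.

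Patients who withdraw early are foreseeable. Protocol 8.3.4.1 says: "Patients with a severe AE at a dose of 0.03 mg/kg or 0.1 mg/kg olipudase alfa will be discontinued from the study and replaced". SAP 2.6.1.6 says: "In this study, if the treatment is discontinued permanently, the patient is withdrawn from the study". Protocol 11.4.2 keeps patients withdrawn for intolerance in the safety population, which is the population for the compliance summaries. The for-cause denominator matters too, because Protocol 8.3.4.2 provides for pauses: "If a potential DLT is observed, dosing will be temporarily stopped in an individual patient".

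What is at stake is the below-80% percentage and the band table. With cohort minimums of 2 to 3 patients in the staggered part of the study (Protocol 6.1), one misplaced patient can visibly change a cohort percentage.

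**Working it through.** **Inputs.** Dosing every 14 days from Day 1, with an infusion at Week 64 (Protocol 8.3.2 and 10.3.8). Week 64 is study day 449, a difference of 448 days from Day 1 (SAP 2.11.4). The window is ±3 days (Protocol 8.3.2 and 8.3.3). W is the number of days from first infusion to withdrawal, and int is the integer part.

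**The plan's own figure.** Infusions at Weeks 0, 2, …, 64: 448/14 + 1 = 33, as the SAP states for completers. The withdrawal formula at the same point: int(448/14) = 32.

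**Shortfall by day of withdrawal.** Infusions are due on days 0, 14, 28 and so on. An infusion whose window is still open at withdrawal counts as expected only if it was given. For every W from 1 to 447, the direct count minus int(W/14) is:

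| Days since latest due date | Situation | Denominator too small by |
|---|---|---|
| 0–3 | that infusion given (always so for Day 1) | 1 |
| 0–3 | that infusion not given | 0 |
| 4–10 | any | 1 |
| 11–13 | next infusion not yet given | 1 |
| 11–13 | next infusion given early | 2 |

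The formula is therefore right in only one situation: withdrawal 0–3 days after a due date other than Day 1, with that infusion not given.

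**Nothing missed, denominator one short.** 2/1 = 200%; 4/3 = 133.3%; 6/5 = 120%; 12/11 = 109.1%. An example of the last is W = 159: int(159/14) = 11, with 12 due and 12 given.

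**Two short.** Infusion due day 154, given day 151, withdrawal day 153: int(153/14) = 10, so 12/10 = 120%.

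**Some missed, denominator one short.** With n due and one missed, the formula gives (n−1)/(n−1) = 100% for every n of 2 or more.

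| Received of due | Correct | SAP formula |
|---|---|---|
| 3 of 4 | 75.0% | 3/3 = 100% |
| 6 of 8 | 75.0% | 6/7 = 85.7% |
| 10 of 13 | 76.9% | 10/12 = 83.3% |

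All three wrongly leave the below-80% band.

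**How general the band error is.** A received count r wrongly leaves that band when r/n < 0.8 and r/(n−1) ≥ 0.8, that is, when 0.8n − 0.8 ≤ r < 0.8n. For n = 2 to 32, exactly one whole number satisfies this unless n is a multiple of 5 (5, 10, 15, 20, 25, 30), when none does. That is 31 − 6 = 25 of 31 values of n.

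**Zero denominators.** For W = 1 to 13, int(W/14) = 0, so a patient with one infusion has 1/0. In the for-cause version, if the second infusion is missed for cause and withdrawal falls on days 18–27, the denominator is 1 − 1 = 0 instead of 2 − 1 = 1.

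**For-cause version otherwise.** Eight due, one missed for cause and one for another reason: 6/(7 − 1) = 100% instead of 6/(8 − 1) = 85.7%. Applied literally to a completer at day 448 with none missed, it gives 33/32 = 103.1%.

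**Check of the corrected rule.** Take int(W/14) + 1. Subtract 1 if withdrawal is 0–3 days after a due date (other than Day 1) and that infusion was not given. Add 1 if withdrawal is 1–3 days before a due date and that infusion was already given. This equals the direct count for every W from 1 to 447. Examples: W = 153 with the early infusion gives 10 + 1 + 1 = 12; W = 156 with the day 154 infusion not given gives 11 + 1 − 1 = 11.

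**The case against.** The strongest objection is that SAP 2.4 does not define the withdrawal date. If the recorded date is well after the last infusion, the missing infusion is offset. A patient who missed nothing and withdraws 14–17 days after the last on-schedule infusion gets exactly 100% under the present formula. Adding 1 might then seem to penalise such patients.

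Under the window rule it does not penalise patients whose next infusion is still in its window. At 14–17 days both rules give 100%. At 30 days after the last infusion, a 4-of-4 patient (W = 72) has int(72/14) = 5 now and 5 + 1 − 1 = 5 under the corrected rule, so 80.0% both ways. A 12-of-12 patient (W = 184) has 13 both ways, 92.3%. At some longer lags the corrected count is higher: at 37 days the 4-of-4 patient (W = 79) goes from 4/5 = 80.0% to 4/6 = 66.7%. That follows the SAP's own definition, which counts everything expected up to withdrawal. What stands is that the date should be defined. The gap affects the present formula as well and does not justify leaving out Day 1. Protocol 10.5.4 asks for the withdrawal visit within 2 weeks of the last infusion where possible, so the short-lag case should be common.

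It can also be said that completers have their own stated value, that the top band admits figures above 100%, and that the results are descriptive. The first and third are true and limit the impact. The second accommodates the error without correcting it, and places patients who missed an infusion in that band.

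**Conclusion.** The concern holds. The formula contradicts the SAP's own count for completers by one and, for most withdrawal dates, understates the infusions expected by one, occasionally by two. Compliance of withdrawn patients can be overstated (up to 200% for two infusions given of two due), a single missed infusion can be hidden, a patient can wrongly leave the below-80% band, and the ratio can be undefined.

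The reach is limited to descriptive compliance percentages and bands for withdrawn patients, plus completers' for-cause figure if that formula is applied to them literally. Completers' overall compliance, the separate counts of missed infusions, the noncompliance definition and the sensitivity analyses that exclude noncompliant patients do not use this formula.

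The day-by-day result assumes due dates fixed relative to Day 1 and the protocol's ±3-day window. The number of patients affected cannot be estimated from the documents. The correction should be made.

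**What to change.** In SAP 2.4, for withdrawn patients, set expected infusions to the integer part of [(date of withdrawal − date of first infusion)/14] **+ 1**, in both denominators. Add one sentence on the window: an infusion whose ±3-day window is still open on the withdrawal date counts as expected only if it was given, and one given early within its window counts as expected. The subtract-1 and add-1 adjustments shown in the check put this into practice.

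Keep 33 for completers, and state that their for-cause denominator is 33 minus the number of infusions missed for cause. State also which recorded date serves as the date of withdrawal.

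The cost is a short text edit and the matching change to the compliance programs, which must relate infusions near withdrawal to their due dates. Data collection does not change, nor does completers' overall compliance.

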2.5 PRIOR AND CONCOMITANT MEDICATION/THERAPY

Medications and therapeutic procedures received by the patient in the 30 days prior to their first infusion until the final visit will be recorded on the Prior and Concomitant Medication the electronic case report form (e-CRF). Medications, including over-the-counter and herbal products as well as supplements, and therapeutic procedures will be collected. Prior and concomitant medications will be coded using the World Health Organization Drug dictionary version dated March of 2019.

- Prior medications will be defined as medications that are taken prior to the first infusion of olipudase alfa in this study.
- Concomitant medications will be defined as medications that are taken on or after the first infusion of olipudase alfa in this study.

A medication that was started before the first infusion but continued beyond the first infusion will be categorized as both prior and concomitant. In case the start/stop date of the medication is missing or incomplete preventing the unambiguous determination of the medication status, the medication will be categorized as both prior and concomitant.

Medication summaries will be presented by WHO-DRUG Anatomic Class and by WHO-DRUG Therapeutic Class for each age group cohort and overall using safety population. Tables will show all medications used during the study, sorted by most prevalent Anatomic Class and then by descending frequency of Therapeutic Class within Anatomic Class based on the prevalence within the overall column.

Prohibited medications include those that are taken during the study and may decrease olipudase alfa activity (eg, fluoxetine, chlorpromazine; tricyclic antidepressants [eg, imipramine, or desipramine]). The medications list with potential prohibited medications will be provided by the data management and will be merged with the concomitant medication data in the database to identify any use of it. Whether the use of such medication constitute a protocol deviation that interferes with assessment of effect of olipudase alfa will be determined by clinical review before the database lock of all prohibited medication intake during the study.

2.6 ANALYSIS OF SAFETY DATA

Safety endpoints include data pertaining to the safety and tolerability of olipudase alfa: assessment of adverse events (AEs)/treatment-emergent adverse events (TEAEs), including AESIs (eg, infusion-associated reactions (IARs), symptomatic overdose, etc.); physical examinations; neurological examinations; clinical laboratory evaluations; vital sign measurements; ECGs; Doppler echocardiography; liver ultrasound Doppler; safety biomarkers; and immune response assessments. For laboratory endpoints, the summaries will use both the international system of units (SI) and US conventional units; figures will use the international system of units (SI); data listings will provide the results in original units as well as in standard units, where applicable.

All the safety analyses will be performed using the safety population. Patients will be summarized and displayed by age group cohorts and overall. Safety data will be reported up to and including the time of treatment withdrawal, and follow-up for AEs, where applicable. The baseline value is the last available value before the first infusion of olipudase alfa, except for white blood cell count, platelet count, hemoglobin and possibly ECG parameters. For complete definition of baseline, refer to [Section 2.11.1](#).

For all safety data, the observation period will be divided into 2 segments:

- The **pretreatment period** is defined as the time between when the patient gives informed consent and the start of the first infusion (excluded).
- The **on-treatment period** is defined as the time from the start of the first infusion (included) till the end of the study.

The following definitions regarding potentially clinically significant abnormality (PCSA) will be applied to laboratory parameters, vital signs and ECG:

The PCSA values are defined as abnormal values considered medically important by the sponsor according to predefined criteria/thresholds based on literature review and defined by the sponsor for clinical laboratory tests, vital signs, and ECG. These values are provided in [Section 2.11.5](#).

- PCSA criteria will determine which patients had at least 1 PCSA taking into account all evaluations performed, including unscheduled or repeated evaluations.
- Before determining a value as PCSA, the value will be rounded to the precision that the PCSA criterion is defined.

2.6.1 Adverse events

2.6.1.1 Definitions

AEs are defined in protocol Section 10.6.1. AEs will be coded according to the version of Medical Dictionary for Regulatory Activities (MedDRA) in use at the time of database lock. Adverse event summaries will include the number of events (N), number (n) and percentage (%) of patients experiencing an adverse event. The denominator for computation of percentages is the safety population for the entire study and for each age group cohort. Sorting order will follow the

internationally agreed MedDRA system organ class (SOC) order, then by decreasing number of patients overall in preferred terms (PTs) within SOCs, and further alphabetically within the same number of patients over different PTs. When more than one PT has same number of events within the same SOC, the order of presentation will be alphabetical in PTs.

The AEs will be classified into different periods of occurrence as follows:

- Pre-treatment adverse events: AEs that started before the start of the first infusion.
- TEAEs: AEs that started during the on-treatment period.

If an AE date/time of onset is incomplete, an imputation algorithm will be used to classify the adverse event within the appropriate adverse event period. The algorithm for imputing date/time of onset will be conservative and will classify an adverse event as treatment emergent unless there is definitive information to determine otherwise. Details on classification of AEs with missing or partial onset dates are provided in [Section 2.11.2](#). If an AE worsens in severity, only the worst severity is captured on the AE log page in the e-CRF.

The AE log page in the e-CRF captures the date when the event became serious. If and when this date is non-missing, it indicates that the AE started as non-serious and became serious after few days. To account for non-serious and serious parts of the AE collected in one AE log page, this AE will be split into two AEs – one non-serious, and one serious AE – with the same AE number, with the following modifications in data for these two AEs:

- Non-serious AE: AE end date, AE outcome, date of death or hospitalization, autopsy information, criterion for serious adverse event (SAE) will be blank.
- Serious AE: AE start date will use the date the event became serious.

Action taken towards study drug and action taken (toward AE) will be considered in relation to the date the event became serious, the last infusion date and dosing information, and a determination will be made, in consultation with safety monitor of the trial, as to whether the recorded fields belong to non-serious AE or serious AE; then the decision will be implemented in analysis. Any such decision will be rationalized in the CSR.

The primary focus of adverse event reporting will be on treatment-emergent adverse events. Pre-treatment adverse events will be listed separately.

Start day of a pre-treatment AE = Start date of AE – first infusion date.

Start day of treatment emergent AE relative to first infusion = Start date of AE – first infusion date + 1.

Start day of treatment emergent AE relative to last infusion = Start date of AE – last infusion date + 1.

2.6.1.2 *Treatment-emergent adverse events*

An overview of TEAEs will be provided by age group cohorts and overall to include (potentially related is defined as either 'related' or 'possibly related' as assessed by the investigator):

- TEAEs.
- TEAEs potentially related to study treatment.
- TEAEs by the worst severity.
- TEAEs leading to treatment discontinuation.
- TEAEs leading to study withdrawal.
- TEAEs leading to dose reduction.
- TEAEs leading to study treatment interruption.
- Protocol-defined IARs.
- Algorithm-defined IARs.
- Treatment-emergent serious adverse events.
- Treatment-emergent serious adverse events potentially related to study treatment.
- TEAEs with fatal outcome (Deaths).
- Treatment-emergent pregnancies.
- TEAEs which are considered symptomatic overdose.
- Dose-limiting toxicities (collected in the adverse event log page in e-CRF, see protocol Section 8.3.4.2.1 for details).

The following summaries will be produced by primary SOC and PT, by age group cohorts and overall:

- TEAEs.
- TEAEs by the worst severity (ie, mild, moderate, or severe).
- TEAEs potentially related to study treatment.

The most common TEAEs are defined as those with percentage of events $\geq 2\%$ and number of patients ≥ 2 in all age cohorts combined. The most common TEAEs by SOC and PT will be provided in descending order of overall incidence by age group cohorts and overall.

TEAEs by the latest infusion dose immediately preceding the start of AE will be provided by SOC and PT, by age group cohorts and overall.

2.6.1.3 *Adverse events of special interest*

The following are AEs of special interest:

Protocol-defined IAR: Any AE that is considered related or possibly related to study treatment as judged by the investigator or the sponsor is defined as a protocol-defined IAR. Sponsor identification will reconcile with investigator identification of IAR before the database lock.

The following summaries will be produced by primary SOC and PT, by age group cohorts and overall:

- Protocol-defined IARs.
- Protocol-defined IARs by the worst severity.
- Protocol-defined IARs started during infusion.
- Protocol-defined IARs started between 0 hours (exclusive) and 3 hours (exclusive) post end of infusion.
- Protocol-defined IARs started between 3 hours (inclusive) and 24 hours (inclusive) post end of infusion.
- Protocol-defined IARs started between 24 hours (exclusive) and 72 hours (inclusive) post end of infusion.
- Protocol-defined IARs started after 72 hours post end of infusion.

Algorithm-defined IAR: All AEs that start between the start of infusion and the end of infusion plus 24 hours are defined as algorithm-defined IARs, irrespective of the perceived relation with study treatment.

The following summaries will be produced by primary SOC and PT, by age group cohorts and overall:

- Algorithm-defined IARs (including any TEAEs with missing time but happened on the same day or the day after the infusion)

A subset of protocol-defined IARs will also be defined programmatically by searching for preferred terms within Hypersensitivity SMQs (identified using SMQ code 20000214 Broad and Narrow scope). The summaries of Hypersensitivity IARs will be provided by primary SOC and PT.

Pregnancy: Pregnancy of a female patient entered in the study as well as pregnancy occurring in female partner of a male patient enrolled in this study is captured as an adverse event. In addition, e-CRF provides urine pregnancy test results as positive or negative. Labs provide serum pregnancy test results. Pregnancies will be provided in the overview of AE summary and the pregnancy test results will be provided as part of patient narrative.

Symptomatic overdose: This is captured as an adverse event in this study. For details, please see Section 10.6.4.1 in the protocol. The symptomatic overdose data will be provided as part of patient narrative.

Asymptomatic overdose: This is captured as an adverse event with verbatim term as 'Asymptomatic overdose'. Asymptomatic overdose data will be provided as part of patient narrative.

Laboratory values: The following protocol-defined potential dose limiting toxicities are also considered AESIs:

- Any increase in AST, ALT, total bilirubin, or AP $>3x$ baseline (before olipudase alfa therapy) and $>$ ULN;
- Any increase in total bilirubin or AP $>1.5x$ baseline, in the presence of AST or ALT $>2x$ ULN;
- Any increase in ALT or AST $>3x$ ULN combined with an increase in ALT or AST $>2x$ baseline (prior to olipudase alfa therapy), with symptoms of fatigue, nausea, vomiting, fever, rash, or eosinophilia ($>$ ULN).

